#### 4.2.2 Exclusion Criteria

A subject must not be enrolled in the study if any of the following criteria are met:

1. Subjects who have any DM-related end-organ damages.
2. Subjects who have a history of diabetic ketoacidosis or hyperosmolar non-ketotic coma.
3. Subjects who have any disease likely to limit life span and/or increase risks of interventions such as:
  - Carotid B-mode ultrasound test results indicating clinically significant stenosis in the common carotid arteries requiring intervention by angioplasty or resection.
  - Cancer treatment in the past 5 years, with the exception of cancers which have been cured, and carry a good prognosis.
  - Infectious disease: HIV positivity, active tuberculosis, or pneumonia.
4. Subjects who have any of the following conditions related to cardiovascular disease:
  - Hospitalization for the treatment of heart disease in the past 12 months.
  - New York Heart Association Functional Class > 2.
  - Left Bundle branch block on ECG at Screening.
  - Third degree atrioventricular block on ECG at Screening.
  - Uncontrolled hypertension with average systolic blood pressure of  $\geq 160$  mmHg or diastolic blood pressure  $\geq 95$  mmHg at Screening and Baseline.
  - Pulse rate  $\geq 95$  beats per minute at Screening and Baseline.
  - Stroke or transient ischemic attack in the past 12 months.
5. Subjects who have any of the following conditions related to gastrointestinal disease:
  - Chronic hepatitis or cirrhosis.
  - Episode of alcoholic hepatitis or alcoholic pancreatitis in the past 2 months.
  - Inflammatory bowel disease requiring treatment in the past 12 months.
  - Significant abdominal surgery (e.g., gastrectomy, gastric bypass) in the past 2 months.
6. Subjects who have serum creatinine  $\geq 1.5$  mg/dL for male or  $\geq 1.4$  mg/dL for female.
7. Subjects who have chronic obstructive airway disease or asthma requiring daily therapy or home use oxygen.
8. Subjects who have hematocrit < 36.0% for male or < 33.0% for female.

9. Subjects who have any of the following conditions or behaviors likely to affect the conduct of the study:
  - Weight loss of > 10% in the past 6 months.
  - Unable to walk without assisted device.
  - Major psychiatric disorder which would impede conduct of the research.
  - Excessive alcohol intake (i.e., more than 2 drinks/day).
10. Subjects who take any of the following medications:
  - Psychoactive agents such as monoamine oxidase inhibitors and antidepressants (e.g., lithium, Prozac, Zoloft, Serzone, Paxil, Effexor).
  - Any other medications that may pose harm to the subject.
11. Female subjects who have a positive serum pregnancy test at Screening, plan a pregnancy during study period, or are breast feeding.
12. Female subjects who don't meet any of the following criteria:
  - Surgically sterile (i.e., have had bilateral tubal ligation, hysterectomy, or bilateral oophorectomy) at least 6 months before randomization.
  - Post-menopausal for at least 12 months prior to Screening.
  - If sexually active, they should use oral contraceptives, double barrier contraception (e.g., condom with spermicide), intrauterine device, or other methods approved by the Sponsor.

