### Schedule of Assessments

*Note: A subject needs to visit the clinical site before breakfast for all study visits except the safety follow-up visit.*

Study Visits 	Screening	Treatment Period							Follow-up
	V1	V2	V3	V4	V5	V6	V7	V8	V9
	Screen (Wk -2)	Baseline (Wk 0)	Wk 2	Wk 4	Wk 6	Wk 8	Wk 10	Wk 12	Wk 14
Informed Consent	X								
Inclusion/Exclusion Criteria	X	X							
Demographic (including height)	X								
Medical/Medication History	X								
Physical Examination	X	X		X		X		X	
Vital Signs and Body Weight	X	X	X	X	X	X	X	X	X
12-lead ECG	X							X	
Blood Sampling for serum chemistry, hematology, FPG, HbA1c, hCG, TSH, T3, and T4 	X	X		X		X		X	
Blood Sampling for zinc, insulin, adiponectin, C-peptide, leptin, glucagon, (CHP in a subset of subjects  )		X		X		X		X	
Urine Sampling for glucose, microalbumin, copper, and zinc		X		X		X		X	
Dispense and Review Daily Log	X	X	X	X	X	X	X	X	
Dispense and Review Medications		X	X	X	X	X	X	X	
Waist Circumference		X		X		X		X	
OGTT 		X						X	
ADDQoL Questionnaire		X						X	
Review of Adverse Event and Concomitant Medication 		X	X	X	X	X	X	X	X

- 1) Visits 3 to 8 have ±3 day visit window and Visit 9 has +7 day visit window.
- 2) Serum chemistry, hematology: Weeks -2, 0, 4, 8, and 12  
HbA1c: Weeks -2, 0, 4, 8, and 12  
FPG: Weeks 0, 4, 8, and 12  
TSH, T3, T4: Weeks 0 and 12  
Serum hCG (pregnancy): Weeks -2 and 12
- 3) CHP levels may be analyzed in a subset of subjects if residual serum and/or plasma samples are available after completion of protocol-required tests.
- 4) See Appendix 1.
- 5) Assess hypoglycemic & hyperglycemic episodes at Visits 2 to 8 only.

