## 5. Study Treatments

### 5.1 Treatment to be Administered

At Visits 2, 3, 4, 5, 6, and 7 (Weeks 0, 2, 4, 6, 8, and 10), each subjects will be dispensed with study drug supply for a 2-week period (14 capsules plus 4 extra capsules, total 18 capsules). The subjects will be instructed to orally administer one capsule just before bedtime each day.

All subjects will be instructed to continue their current diabetes medications and all other prescribed drugs.

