### 6.1 Screening Period

A screening visit will occur at least 2 weeks prior to the randomization.

A signed and dated Institutional Review Board (IRB) approved Informed Consent Form must be obtained before any study-specific procedures are performed. Once written informed consent has been obtained, the following screening procedures and assessments must be performed to determine eligibility and document adherence to the preliminary inclusion/exclusion criteria:

- Record demographic data (i.e., date of birth, race, and height).
- Record relevant medical history including diabetic history.
- Record details of previous medications.
- Perform a physical examination.
- Measure vital signs (sitting blood pressure, pulse, breathing, and temperature) and weight.
- Measure 12-lead ECG.
- Collect blood samples for hematology, serum chemistry, HbA1c, and pregnancy test (serum hCG).
- Dispense daily log with blood glucose monitoring devices to record daily blood glucose values (fasting before breakfast and two hours after dinner) and study medication adherence (See Appendix 2).

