### 6.2 Treatment Period

#### 6.2.1 Visit 2 (Week 0): Baseline

Visit 2 will occur after the completion of 2-week assessment (+7 days). During this visit, the following procedures and assessments must be performed:

- Measure vital signs (sitting blood pressure, pulse, breathing, and temperature) and weight.
- Perform a physical examination.

- Collect daily logs and blood glucose monitoring devices and review daily logs with the subject.
- Record any changes in concomitant medications.
- Record an adverse event, if applicable.
- Assess hypoglycemic and hyperglycemic episodes (See Appendix 4).
- Confirm the inclusion and exclusion criteria.
- Randomize the subject
- Conduct the ADDQoL Questionnaire (See Appendix 3).
- Perform the OGTT (See Appendix 1)
- Measure waist circumference.
- Collect blood samples for hematology, serum chemistry, HbA1c, FPG, and thyroid function test (TSH, T3, and T4).
- Collect blood samples\* for zinc, insulin, adiponectin, C-peptide, leptin, and glucagon.
- Collect urine samples for glucose, microalbumin, copper, and zinc.
- Dispense study medications to the subject with detailed instructions.
- Dispense daily log with blood glucose monitoring devices to record daily blood glucose values (fasting before breakfast and two hours after dinner) and study medication adherence (See Appendix 2).

\*If residual plasma and/or serum are available, CHP levels may be measured.

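### The pregnancy exclusion rests on a serum test taken 14 to 21 days before randomization, so the Visit 2 eligibility check gives no current pregnancy result

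*Protocol*

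**What the plan says.** Exclusion 11 (Protocol 4.2.2, same wording in SAP 3.2.2) excludes "Female subjects who have a positive serum pregnancy test at Screening, plan a pregnancy during study period, or are breast feeding". The Screening list in Protocol 6.1 includes the test: "Collect blood samples for hematology, serum chemistry, HbA1c, and pregnancy test (serum hCG". The same section says "A screening visit will occur at least 2 weeks prior to the randomization", and Protocol 6.2.1 says "Visit 2 will occur after the completion of 2-week assessment (+7 days".

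At Visit 2 the site must "Confirm the inclusion and exclusion criteria", randomize the subject and dispense study drug. The safety and thyroid blood draw at that visit is "Collect blood samples for hematology, serum chemistry, HbA1c, FPG, and thyroid function test (TSH, T3, and T4", without hCG. Urine is collected for glucose, microalbumin, copper and zinc.

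The blood-sampling row of the Schedule of Assessments names hCG and is marked at Visit 2, but footnote 2 restricts it: "Serum hCG (pregnancy): Weeks -2 and 12". The SAP schedule (3.1.2) carries the same row and footnote. Protocol 6.2.4 lists serum hCG at Visit 8 and applies the same list to an Early Termination visit. The lists for Weeks 2 to 10 contain no pregnancy test.

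**The concern.** Confirming eligibility at Visit 2 should establish that the subject is eligible when she is about to be dosed. For pregnancy it only confirms a result that is two to three weeks old. The plan itself treats pregnancy as important: it is an exclusion, it must be reported on the same timelines as an SAE (Protocol 9.4), and it is tested again at Week 12. For a subject who completes treatment, that later test can only reveal exposure after it has happened.

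Two things are at stake. The first is avoidable fetal exposure to an investigational product for up to about 12 weeks. The second is data quality. Both co-primary endpoints, change in HbA1c and change in body weight, would be confounded by pregnancy in an affected subject, and each arm has only 16 subjects.

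**Working it through.** The plan states no figure for these intervals, so there is none to reproduce. The check is date arithmetic on the stated visit windows, followed by a comparison of the passages.

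**Inputs**
- Screening to randomization, minimum: 2 weeks = 14 days (Protocol 6.1).
- Screening to Visit 2, maximum: 14 + 7 = 21 days (Protocol 6.2.1).
- Treatment: 12 weeks = 12 × 7 = 84 days.
- Window for Visits 3 to 8: ±3 days. Protocol 4.1 and 6 and footnote 1 of the schedule tie it to the schedule from randomization. Protocol 6.2.2 to 6.2.4 tie it to the previous visit.
- First dose: taken as the evening of Visit 2. This is an inference: drug is dispensed at that visit, and Protocol 5.1 says "The subjects will be instructed to orally administer one capsule just before bedtime each day".

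**Screening hCG to randomization and first dose:** 14 to 21 days.

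**Screening hCG to Week 12 hCG, for a completer**
- No visit window applied at Week 12: 14 + 84 = 98 to 21 + 84 = 105 days.
- ±3 days around the fixed Week 12 date: 14 + 81 = 95 to 21 + 87 = 108 days.
- ±3 days from each previous visit, over six two-week steps of 11 to 17 days: 14 + 6 × 11 = 80 to 21 + 6 × 17 = 123 days.

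On every reading, the whole period from first dose to Visit 8 passes without a required test.

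**Who passes the criterion as written**
- Conceived after the Screening sample: the Screening test is negative, no test follows at Visit 2, and she can be randomized.
- Conceived too shortly before the Screening sample to test positive: the same path.

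**Comparison within the protocol.** In exclusion 4 the blood pressure and pulse limits refer to both Screening and Baseline. In exclusion 11 the pregnancy test refers to Screening only. The Visit 2 check thus has new measurements for exclusion 4 but no new pregnancy test result for exclusion 11.

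**Order of steps at Visit 2.** Protocol 6.2.1 lists randomization before the blood and urine samples. If the list is followed in order, a result from those samples would come too late to affect eligibility.

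**The case against.** The strongest reply is that the documents agree on test timing and that testing is not the only safeguard.

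- A reader might infer that exclusion 11 cannot be confirmed at Visit 2. That is not so. Its test element is the Screening result, which is on file, and pregnancy plans and breast feeding can be asked about. What is missing is current pregnancy status.
- A reader might infer from the marked row at Visit 2 that the schedule contradicts itself. Footnote 2 settles which weeks apply to hCG, and the visit lists follow it. The shared row is easy to misread, no more.
- Exclusion 12 requires surgical sterility, post-menopausal status or, if sexually active, contraception. This narrows the group at risk to women of childbearing potential and lowers the chance of pregnancy. It sets no minimum period of contraceptive use before Screening, and it cannot rule out failure, non-adherence or a conception just before Screening.
- Week 12 is not the only later test. Early Termination includes serum hCG, and Protocol 6 and 6.4 let the investigator add procedures. The first helps only those who leave early, and the second is discretionary.
- It is tempting to argue that the 49-volunteer single-dose study in Protocol 1.3 is the only human experience. Protocol 5.8 also mentions an earlier informal study, and the Investigator's Brochure is not available here. The point does not need that argument.
- Saying that a pregnancy invalidates the co-primary endpoints would go too far. It would confound one subject's values. That subject is 1/16 = 6.25% of an arm, which says nothing about how often this would occur.

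These replies limit the claim. None of them supplies a pregnancy result between Screening and the first dose.

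**Conclusion.** The point holds as a gap in eligibility checking. The plan requires no pregnancy test in the 14 to 21 days between the Screening sample and randomization. For completers it requires none until Week 12, an interval of 95 to 108 days with the window around the fixed Week 12 date, or 80 to 123 days with windows running from each previous visit. The conclusion is the same on either reading.

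It rests on footnote 2 governing the schedule row, and it concerns only women who could become pregnant. The documents give neither the share of such women nor a pregnancy rate, so the expected number affected cannot be calculated and may be small. The case for a change is that a possible and avoidable exposure can be prevented at very low cost.

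**What to change.** Reconcile exclusion 11, the Visit 2 eligibility check and footnote 2, in both the protocol and the SAP:

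- Re-check pregnancy at Visit 2 in women who are neither surgically sterile nor post-menopausal, using the urine already collected there.
- State in Protocol 6.2.1 that this sample and its result come before the randomization step, since sampling is now listed after it.
- Reword exclusion 11 to cover Screening and Baseline, as exclusion 4 does for blood pressure and pulse, and make clear that a positive result at either visit excludes.
- Update footnote 2 so that the schedule row and the visit lists agree.

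The cost is a few test kits, slightly longer handling at Visit 2 and a short amendment, with no extra visit or blood draw. Whether to test again during treatment goes beyond the eligibility question and is for the sponsor to decide.

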### **4.3 Subject Withdrawal**

Any subject is free to withdraw from participation in the study at any time, for any reason, specified or unspecified, and without prejudice to further treatment. The criteria for enrollment are to be followed explicitly. If a subject who does not meet enrollment criteria is inadvertently enrolled, that subject should be withdrawn from the study and the Sponsor/contract research organization (CRO) must be contacted. An exception may be granted in rare circumstances where there is a compelling reason to allow the subject to continue. In these rare cases, the investigator must obtain documented approval from the Sponsor or Sponsor designee to allow the subject to continue in the study.

In addition, subjects will be withdrawn from study drug and from the study in the following circumstances:

- The investigator decides that the subject should be withdrawn. If this decision is made because of an intolerable AE or a clinically significant laboratory value, if the dose of study drug has not been administered, it will be withheld and appropriate measures are to be taken. The Sponsor or Sponsor designee is to be notified immediately.
- The subject is unwilling to continue in the study.
- The subject is not compliant with the protocol.
- The investigator or the Sponsor, for any reason, stops the study.

If a subject prematurely withdraws from the study, every effort must be made to have the subject return to the clinical site for a premature termination visit. In all cases, the reason for withdrawal must be recorded in the Electronic Case Report Form (eCRF) and in the subject's medical records.

Contact will be maintained with subjects who are removed due to an AE until it has been resolved or stabilized, and the information will be documented in the eCRF and in the subject's medical records.

#### **4.4 Premature Termination of Study / Closure of Center**

The Sponsor has the right to terminate this study, and the investigator/Sponsor has the right to close a clinical site, at any time, although this should occur only after consultation between involved parties; the IRB must be informed in any case. Should the clinical site be closed prematurely, all study materials (e.g., study medication) must be returned to the Sponsor.

Discontinuation of the study may be necessary for medical or administrative reasons such as:

- Serious adverse events probably related to study drug administration so that the use of study drug may no longer be justifiable
- Significant change of benefit-risk ratio for the subjects
- The enrollment period has been exceeded
- The Sponsor discontinues the investigation of Cyclo-Z for type 2 diabetes indication or determines that the doses being studied are no longer justifiable

Possible reasons for closing of a clinical site include the following:

- The investigator feels that the number or severity of adverse events is excessive
- A change of technical, administrative, or personal circumstances occurs and the conduct of the study no longer meets ICH-GCP guidelines
- In case of evident, significant non-compliance to protocol or poor data quality
- The enrollment rate at a clinical site is unlikely to result in the recruitment of the required subject numbers.

## 5. Study Treatments

### 5.1 Treatment to be Administered

At Visits 2, 3, 4, 5, 6, and 7 (Weeks 0, 2, 4, 6, 8, and 10), each subjects will be dispensed with study drug supply for a 2-week period (14 capsules plus 4 extra capsules, total 18 capsules). The subjects will be instructed to orally administer one capsule just before bedtime each day.

All subjects will be instructed to continue their current diabetes medications and all other prescribed drugs.

### 5.2 Identity of Investigational Product

Investigational products are white-color capsules and supplied to clinical sites in HDPE bottles. Placebo capsules will be matched for Cyclo-Z capsules in color, shape, and size and will be indistinguishable from Cyclo-Z capsules. All manufacturing and packaging activities will be performed according to cGMP guidelines.

Each bottle has a label including the following information:

- Product name
- Randomization number
- Dosage form information
- Protocol number
- Lot number
- Dosing instruction
- Storage condition
- Cautionary statement
- Sponsor name and contact information

All drug supplies must be stored in a secure area (e.g., locked cabinet), at controlled room temperature 15~30 °C (59~86 °F).

### 5.3 Randomization

At Visit 2 (Week 0), subjects who meet the inclusion/exclusion criteria will be randomly assigned to receive placebo or 1 of 3 doses of Cyclo-Z in accordance with the randomization code, which will be generated by the Sponsor. Specifically, the subjects will be randomly assigned in a 1:1:1:1 ratio to the following:

- Dose A: Cyclo-Z containing 23 mg zinc plus 3 mg CHP – 16 subjects
- Dose B: Cyclo-Z containing 23 mg zinc plus 9 mg CHP – 16 subjects

- Dose C: Cyclo-Z containing 23 mg zinc plus 15 mg CHP – 16 subjects
- Dose D: Placebo – 16 subjects

#### **5.4 Selection of Doses in the Study**

The doses of Cyclo-Z were chosen on the basis of results of non-clinical efficacy and safety studies. The detailed results are documented in the Investigator's Brochure.

#### **5.5 Choice of Controls/Comparators**

This study uses an inert placebo as a negative control. The purpose of this is to reduce all potential influences on the actual or apparent course of the disease other than those arising from the pharmacologic or toxicological action of the study medication.

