### Combination of CHP and zinc in the treatment of diabetes via stimulation of IDE synthesis:

Insulin degrading enzyme (IDE) is a zinc-containing enzyme that regulates degradation of internalized insulin and the maintenance of insulin sensitivity. Diabetic animals and humans are zinc deficient due to impaired intestinal zinc absorption and hyperzincuria. Insulin bound to its receptor is transported to the endosome where it is separated from the insulin receptor. The inactive insulin is degraded to peptides and amino acids by IDEs. Under normal conditions, incompletely digested peptides in the endosome are completely digested in the lysosome. Incomplete digestion of the used insulin can interfere with the propagation of insulin-receptor-initiated signal transduction processes, thereby inducing insulin resistance (Fig. 1 below). If endosomal IDE levels are inadequate, undigested insulin will remain in the cytosol and prevent insulin signal transduction thereby disrupting the synthesis or translocation of glucose transporter-4 (GLUT-4) to the cell membrane for glucose uptake. Cyclo-Z enhances IDE synthesis and stimulates insulin degradation. Although Cyclo (his-pro) (CHP) or zinc alone are somewhat effective in the control of blood glucose metabolism, we hypothesize, based on the available literature and previous background studies, that the combination of CHP and zinc in Cyclo-Z work synergistically to ameliorate insulin resistance in diabetic and obese patients mainly by stimulating IDE synthesis.

[figure not shown]

Figure 1: Degradation of Used Insulin in the Muscle and Fat Cells

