## **2. Study Objective(s)**

### **2.1 Primary Objective**

The primary objective is to assess the dose-dependent efficacy of Cyclo-Z for the treatment of subjects with obese type 2 diabetes.

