### 5. HYPOTHESES

The primary objective is to assess the dose-dependent efficacy of Cyclo-Z for the treatment of subjects with obese type 2 diabetes. The hypothesis of this study is set as follows.

The dose-dependent efficacy of Cyclo-Z will be demonstrated by identifying statistically significant difference in the change of HbA1c level and BW from baseline at Week 12 in Dose A, B, C, and D using one-way analysis of variance (ANOVA) methods. Specifically, all three experimental groups will be compared to the control group on the change: Dose A vs. D, B vs. D, and C vs. D.

$$H_0: \mu_A = \mu_B = \mu_C = \mu_D$$

$$H_1: \text{not } H_0$$

$\mu$ : the mean of the primary clinical efficacy variables by each of the four dose groups

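### SAP section 5 would declare dose dependence from a step off placebo that is equal in all three active arms; only comparisons among A, B and C hold zinc constant, and none is planned

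*Protocol*

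**What the plan says.** Protocol 2.1 (repeated in SAP 2.1) sets the aim: "The primary objective is to assess the dose-dependent efficacy of Cyclo-Z". Protocol 5.3 and SAP 3.4.1 list four arms with 16 in each. The lowest active arm reads "Dose A: Cyclo-Z containing 23 mg zinc plus 3 mg CHP". Arms B and C keep zinc at 23 mg and raise CHP to 9 and 15 mg, and the fourth arm, labelled D, is placebo.

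Protocol 5.5 describes the comparator: "This study uses an inert placebo as a negative control". Neither document says in terms that placebo is zinc-free. I infer it from the word inert and from an arm list that names zinc only for A, B and C.

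The background in Protocol 1.2 contains the clause "Although Cyclo (his-pro) (CHP) or zinc alone are somewhat effective in the control of blood glucose metabolism".

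SAP section 5 takes dose-dependent efficacy to be shown through "identifying statistically significant difference in the change of HbA1c level and BW from baseline at Week 12 in Dose A, B, C, and D". The method is one-way ANOVA with the null hypothesis that all four means are equal. It adds the comparisons A, B and C each against D. SAP 10.5.1 runs the latter by Dunnett's test. SAP 10.5.1 to 10.5.3 plan no comparison among A, B and C and no trend test; Protocol 8.1.3 likewise compares only with the control group.

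**The concern.** Between A, B and C, dose means CHP alone, since zinc is fixed at 23 mg. Between D and A, two things change: zinc goes from 0 to 23 mg and CHP from 0 to 3 mg. The rule in SAP section 5 pools both kinds of difference and attaches the words dose-dependent efficacy to the result.

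Suppose A, B and C share one mean and differ from D. The response over 3 to 15 mg CHP is then flat. The ANOVA null is still false, as are all three nulls against D, so the plan's rule would be met with no dose gradient among the doses studied. The protocol supplies one candidate cause, since it regards zinc alone as having some effect on blood glucose. A CHP effect that has levelled off by 3 mg would give the same pattern.

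At stake is the primary objective itself. A conclusion of dose dependence would go into the choice of CHP dose for later work, while the only contrasts that bear on CHP dose at constant zinc had not been examined.

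**Working it through.** **Inputs from the documents.** Four arms of 16, so 4 × 16 = 64 subjects, as stated. Error df with all subjects observed: 4 × (16 − 1) = 60. Significance level 0.05 (SAP 10.1), taken as two-sided because sidedness is not stated. There is no power calculation to reproduce: Protocol 8.2 and SAP 3.3 say that the number was not based on one.

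**Assumption.** The documents give no SD for the change and no zinc effect. I set the means to e in A, B and C and 0 in D, with e in SD units. The values 0.39 and 0.56 match the HbA1c falls that Protocol 1.1 cites for a DPP-4 inhibitor if the SD were 1.0 point; 0.80 is a larger illustrative value. The range shows sensitivity and does not predict what zinc does. For body weight the documents give no basis for any value.

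**Planned four-group ANOVA.** The overall mean is 0.75e, so the sum of squared deviations is 3 × (0.25e)² + (0.75e)² = 0.75e². The noncentrality is 16 × 0.75e² = 12e², that is 1.83, 3.76 and 7.68. Power comes from the noncentral F with 3 and 60 df.

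**Planned Dunnett tests.** Critical value 2.41, from 400,000 simulated trials. The result is the chance that at least one of A, B and C differs significantly from D.

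**Linear CHP contrast within A to C.** The doses 3, 9 and 15 mg are equally spaced, so the coefficients are −1, 0, +1 and the contrast equals C minus A. Its expectation is e − e = 0, so it rejects at its nominal rate whatever the step.

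| Equal step e (SD) | ANOVA rejects | At least one Dunnett rejects | CHP contrast within A–C rejects |
|---|---|---|---|
| 0.39 | 17% | 22% | 5% |
| 0.56 | 32% | 40% | 5% |
| 0.80 | 60% | 69% | 5% |

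The 5% holds by construction. It shows that the contrast is not moved by an equal step; it does not show that the contrast is powerful.

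**What the contrast can detect.** SE of C minus A = √(2/16) = 0.354 SD. The 95% half-width is 2.00 × 0.354 = 0.71 SD. For true C minus A differences of 0.39, 0.56 and 0.80 SD, the noncentralities are 1.10, 1.58 and 2.26 (difference ÷ 0.354), and power by the noncentral t with 60 df is about 19%, 34% and 61%.

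**The case against.** The strongest reply is that Cyclo-Z is the combination. Protocol 1.2 describes a capsule of CHP and zinc, and the objective concerns that product and not CHP by itself. Inert placebo is then the proper zero, and any zinc effect is rightly credited to Cyclo-Z. This stands. A reader might infer that the control is wrong or confounded, but Protocol 5.5 contains no error, and A, B and C against D are valid tests of zinc plus CHP against placebo. What the reply does not rescue is the use of those tests to show dependence on dose.

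A reader might also infer that the trial fails to test the synergy put forward in Protocol 1.2. Synergy is background there; it is not an objective, endpoint or hypothesis. Nor is an ordered trend with placebo as the lowest dose planned, so the point does not rest on one.

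It is fair to say that the figures are not specific to zinc. They describe any equal step, including a CHP plateau by 3 mg with zinc inert, and the data cannot tell these apart. For the same reason, extending the A-to-C line back to 0 mg CHP should not be offered as a zinc estimate. Take zinc as inert and CHP following an Emax curve with an assumed ED50 of 3 mg. The responses at 3, 9 and 15 mg are 0.50, 0.75 and 0.83 of Emax, with mean 0.694 and slope (0.833 − 0.500)/12 = 0.0278 per mg. The line at 0 mg then gives 0.694 − 9 × 0.0278 = 0.44 of Emax, all wrongly called zinc.

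Finally, this is an exploratory, unpowered phase 2 study. That excuses imprecision. It does not excuse a rule that can declare dose dependence from a flat response. The dose rationale sits in the Investigator's Brochure, which I have not seen, but it could not alter what these tests measure.

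**Conclusion.** The concern holds for the inference rule in SAP section 5 and not for the choice of control. The rule counts any difference from placebo as dose-dependent efficacy, and the plan omits the comparisons that hold zinc constant. With an equal step of 0.39 to 0.80 SD and no gradient over 3 to 15 mg, the planned ANOVA would support the claim in 17% to 60% of trials and at least one Dunnett comparison in 22% to 69%.

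These sizes rest on an assumed step, 16 evaluable subjects per arm, equal variances, normal errors and a zinc-free placebo. The direction holds for any nonzero equal step. The documents do not show that zinc has such an effect in this population, only that the protocol considers zinc somewhat active on blood glucose.

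**What to change.** In SAP sections 5 and 10.5.1:

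1. Keep the four-group ANOVA and the Dunnett tests, described as evidence of efficacy of Cyclo-Z against placebo only.
2. For HbA1c and body weight, add the linear CHP contrast over 3, 9 and 15 mg from A, B and C, using the four-group error term, and report it with its 95% CI.
3. Rest any statement about dose dependence on that contrast.
4. State that comparisons with placebo do not separate CHP from zinc, and do not present an extrapolation to 0 mg CHP as a zinc effect.

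The cost is SAP wording and one contrast for each of the two primary variables, on data already collected; no arm, subject or procedure is added. The price is that dose dependence becomes harder to claim, given the half-width and power shown above. The SAP should therefore also say that a non-significant slope is not evidence of no dose effect.
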